 5. Any suicidal ideation with intent with or without a plan, at the time of or within 6 months of Screening, as indicated by answering “Yes” to questions 4 or 5 on the Suicidal Ideation section of the C-SSRS.
 6. Any suicidal behavior in the past based on the C-SSRS (revised per Amendment 01)
 7. Any history of anorexia or bulimia within 2 years before Screening, Attention Deficit Hyperactivity Disorder, any Diagnostic and Statistical Manual of Mental Disorders, 5th Edition depressive disorder, suicidal ideation or behavior, bipolar disorder, or schizophrenia
 8. Known secondary causes (genetic, endocrine, or metabolic) for obesity (eg, Prader-Willi syndrome, Bardet Biedl syndrome, Down’s Syndrome, untreated hypothyroidism, Cushing’s syndrome, daily systemic corticosteroid exposure for longer than 30 days, history of significant exposure to corticosteroids for chronic illness during the past year)
 9. Use of other products intended for weight loss including prescription drugs, over-the-counter (OTC) drugs, and herbal preparations within 1 month before Screening
 10. Use of any of the following medications:
 - a) Serotonergic drugs within 7 days (or 5 half-lives, whichever is longer) or monoamine oxidase inhibitors (MAOIs) within 30 days before Randomization, including:
 - selective serotonin reuptake inhibitors (SSRIs)
 - serotonin norepinephrine reuptake inhibitors (SNRIs)
 - tricyclic antidepressants (TCAs)
 - bupropion
 - triptans
 - St. John’s Wort
 - tryptophan
 - linezolid
 - dextromethorphan in any form (eg, OTC cold medicines)
 - lithium
 - tramadol
 - antipsychotics or other dopamine antagonists
 - b) Others
 - antiseizure medications including valproic acid, zonisamide, topiramate, and lamotrigine
 - oral steroids (topical and inhaled steroids are acceptable)
 - stimulant medications (eg, Ritalin, Concerta, Biphedamine, and Dexedrine)
 - benzodiazepines
 11. Use of drugs known to increase the risk for cardiac valvulopathy within 6 months before Screening,

- including but not limited to pergolide, ergotamine, methysergide, and cabergoline

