 28. Female subjects who are breastfeeding or pregnant at Screening or Baseline (as documented by a positive β -human chorionic gonadotropin test). A separate Baseline assessment is required if a negative screening pregnancy test was obtained more than 72 hours before the first dose of study drug.
 29. Female subjects of childbearing potential who:
 - a. Had unprotected sexual intercourse within 30 days before study entry and who do not agree to use a highly effective method of contraception (eg, total abstinence, an intrauterine device, a double-barrier method [such as condom plus diaphragm with spermicide], a contraceptive implant, an oral contraceptive, or have a vasectomized partner with confirmed azoospermia) throughout the entire study period and for 28 days after study drug discontinuation
 - b. Are currently abstinent and do not agree to use a double-barrier method (as described above) or refrain from sexual activity during the study period and for 28 days after study drug discontinuation
 - c. Are using hormonal contraceptives, but are not on a stable dose of the same hormonal contraceptive product for at least 4 weeks before dosing and who do not agree to use the same contraceptive during the study and for 28 days after study drug discontinuation
- (NOTE: All female subjects will be considered to be of childbearing potential unless they have been sterilized surgically [ie, bilateral tubal ligation, total hysterectomy, or bilateral oophorectomy, all with surgery at least 1 month before dosing]).

Study Treatment(s)**Test drug**

Belviq XR (lorcaserin hydrochloride) will be provided as orange-colored, round, film-coated, biconvex tablets with one 20-mg tablet administered orally QD.

Comparator Drug

Matching placebo, 1 tablet administered orally QD

Duration of Treatment

Prerandomization Phase: up to 30 days

Randomization Phase: approximately 56 weeks

Concomitant Drug/Therapy

Other products intended for weight loss, including prescription drugs, OTC drugs, and herbal preparations, are prohibited as concomitant medications. OTC cold medicines containing dextromethorphan can be used for up to 7 days with study medication temporarily stopped for that time period and resumed the next day after the OTC cold medicine is stopped. Any of the following serotonergic agents or other agents in combination with Belviq XR are prohibited:

Serotonergic drugs

- SSRIs
- SNRIs
- TCAs
- bupropion
- triptans
- St. John's Wort
- tryptophan
- MAOIs
- linezolid

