- Proportion (%) of subjects achieving at least a 5% and at least a 10% reduction in BMI

Other PD endpoints will be considered based on the data at the end of the study to explore their relationships with lorcaserin plasma exposure.

Pharmacogenomic/Pharmacogenetic Assessments

Not applicable

Safety Assessments

Safety assessments will consist of monitoring and recording all adverse events (AEs) and serious adverse events (SAEs); electrocardiograms (ECGs); laboratory evaluation for hematology, metabolic function (fasting glucose, fasting lipids, and thyroid), adrenal function and biochemical blood and urine bone health assessments; blood chemistry and urine values; neuropsychiatric events; periodic measurement of vital signs, neuromuscular signs for screening potential serotonin syndrome, and signs or symptoms of priapism and hyperprolactinemia; and performance of physical examinations. In patients with potential prolactin-related AEs, such as galactorrhea, changes in libido, or changes to menstrual cycle, prolactin level will be measured and assessed.

Other Safety Assessments

Effect on growth will be evaluated using the CDC growth chart and bone age determination by x-ray of the hand. Sexual maturation will be evaluated by assessing sex hormones and Tanner Staging.

The C-SSRS will be used to assess all subjects in the study for any signal of depression or suicidal ideation or behavior at every visit. Additionally, screening, diagnosing, monitoring, and measuring the severity of depression will be assessed using the PHQ-9 and effects on cognition will be assessed using the Leiter-3. (revised per Amendment 01)

Echocardiographic assessments will be used to exclude subjects with FDA-defined valvulopathy, pulmonary hypertension, and other major cardiovascular disease (as outlined in Exclusion Criterion No. 3) during the Screening Period. Additionally, cardiac valvular function and pulmonary systolic pressure changes at Weeks 28 and 52 will be assessed. Valvular regurgitation as assessed in the echocardiogram will be rated absent, trace, mild, moderate, or severe for the aortic, mitral, and tricuspid valves; the rating will be absent or present for the pulmonic valve. The evaluations will be based on guidelines from the American Society of Echocardiography. Pulmonary artery pressure will be estimated from the TR jet velocity.

Bioanalytical Methods

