 8. Known secondary causes (genetic, endocrine, or metabolic) for obesity (eg, Prader-Willi syndrome, Bardet Biedl syndrome, Down’s Syndrome, untreated hypothyroidism, Cushing’s syndrome, daily systemic corticosteroid exposure for longer than 30 days, history of significant exposure to corticosteroids for chronic illness during the past year)
 9. Use of other products intended for weight loss including prescription drugs, over-the-counter (OTC) drugs, and herbal preparations within 1 month before Screening
 10. Use of any of the following medications:
 - a) Serotonergic drugs within 7 days (or 5 half-lives, whichever is longer) or monoamine oxidase inhibitors (MAOIs) within 30 days before Randomization, including:
 - selective serotonin reuptake inhibitors (SSRIs)
 - serotonin norepinephrine reuptake inhibitors (SNRIs)
 - tricyclic antidepressants (TCAs)
 - bupropion

- triptans
 - St. John's Wort
 - tryptophan
 - linezolid
 - dextromethorphan in any form (eg, OTC cold medicines)
 - lithium
 - tramadol
 - antipsychotics or other dopamine antagonists
- b) Others
- antiseizure medications including valproic acid, zonisamide, topiramate and lamotrigine
 - oral steroids (topical and inhaled steroids are acceptable)
 - stimulant medications (Ritalin, Concerta, Biphedamine and Dexedrine)
 - benzodiazepines
11. Use of drugs known to increase the risk for cardiac valvulopathy within 6 months before Screening, including but not limited to pergolide, ergotamine, methysergide, and cabergoline
 12. History or evidence of clinically significant disease (eg, malignancy; cardiac, respiratory, gastrointestinal, renal, or psychiatric disease) other than prediabetes (impaired fasting glucose or impaired glucose tolerance), Type 2 diabetes treated with oral anti-diabetic agents (excluding sulfonylurea) or non-insulin injectable antidiabetic agents, obstructive sleep apnea, dyslipidemia, and nonalcoholic fatty liver disease
 13. Use of Belviq XR within 6 months before Screening or hypersensitivity to Belviq XR or any of the excipients
 14. Significant change in diet or level of physical activity within 1 month before dosing or change in weight of more than 5 kg within 3 months before Screening
 15. Any use of a of very-low-calorie (<1000 calories/day) weight loss diet within 6 months before Screening
 16. History of alcohol or drug dependence or abuse
 17. Recreational drug use within 2 years before Screening
 18. Known to be human immunodeficiency virus positive

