9.4.6 Prior and Concomitant Therapy

Any medication (including OTC medications) or therapy administered to the subject during the study (starting at the date of informed consent) will be recorded on the Prior and Concomitant Medication Case Report Form (CRF) or Non-Pharmacological Procedures CRF. The investigator will record on the Adverse Event CRF any AE for which the concomitant medication/therapy was administered. If the concomitant medication/therapy is

being administered for a medical condition present at the time of entry into the study, the investigator will record the medical condition on the Medical History and Current Medical Condition CRF.

Other products intended for weight loss including prescription drugs, OTC drugs, and herbal preparations are prohibited as concomitant medications. OTC cold medicines containing dextromethorphan can be used for up to 7 days and study medication is temporarily stopped for that time period and resumed the next day after the OTC cold medicine is stopped. Any of the following serotonergic agents in combination with Belviq XR is prohibited:

a. Serotonergic drugs

- SSRIs
- SNRIs
- TCAs
- bupropion
- triptans
- St. John's Wort
- tryptophan
- MAOIs
- linezolid
- dextromethorphan
- lithium
- tramadol
- antipsychotics or other dopamine antagonists

b. Others

- antiseizure medications including valproic acid, zonisamide, and lamotrigine
- oral steroids (topical or inhaled steroids are acceptable)
- stimulant medications (Ritalin, Concerta, Biphedamine and Dexedrine)
- benzodiazepines

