9.7.1.8.1 EXTENT OF EXPOSURE

Subjects will receive Belviq XR 20 mg or placebo QD for up to 52 weeks. The extent of exposure will be characterized by duration of exposure (in weeks) for each treatment group.

Duration of exposure will be defined as the number of weeks between the date the subject received the 1st dose of study drug and the date the subject received the last dose of study drug. Duration of exposure will be summarized using descriptive statistics by treatment group. In addition, the duration of exposure will be categorized and will be summarized using frequency count by treatment group.

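### The on-study prohibited-drug lists omit the valvulopathy-risk drugs that exclusion 11 bars before Screening (protocol v7.0)

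*Protocol*

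**What the plan says.** Section 9.3.2, exclusion 11, bars "Use of drugs known to increase the risk for cardiac valvulopathy within 6 months before Screening, including but not limited to pergolide, ergotamine, methysergide", and then names cabergoline as a fourth example. The synopsis has the same criterion under the same number: "Use of drugs known to increase the risk for cardiac valvulopathy within 6 months before Screening". In both places the restricted period ends at Screening.

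What a subject may not take during the study is set out in Section 9.4.6 and under Concomitant Drug/Therapy in the synopsis. Section 9.4.6 first bars weight-loss products: "Other products intended for weight loss including prescription drugs, OTC drugs, and herbal preparations are prohibited as concomitant medications". It then gives an itemised list under the lead-in "Any of the following serotonergic agents in combination with Belviq XR is prohibited". The synopsis gives the same items under "Any of the following serotonergic agents or other agents in combination with Belviq XR are prohibited".

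On duration, Section 9.7.1.8.1 says "Subjects will receive Belviq XR 20 mg or placebo QD for up to 52 weeks". On valve safety, the synopsis says "cardiac valvular function and pulmonary systolic pressure changes at Weeks 28 and 52 will be assessed". Section 9.7.1.8.6 summarises FDA-defined valvulopathy by treatment group at those two weeks, and Section 9.5.1.5.2 makes new-onset valvular heart disease a serious event in every case.

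**The concern.** The protocol treats recent use of these drugs as incompatible with entry, but says nothing about their use alongside study drug, when the two exposures would coincide. The drugs in exclusions 9 and 10 are barred both before entry and on treatment; those in exclusion 11 are barred only before entry.

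Two things are at stake. An adolescent could acquire a second, avoidable valve risk while taking study drug. If a new valve lesion then appeared at the Week 28 or Week 52 echocardiogram, its cause would be harder to assign. In addition, because the lists do not prohibit use, taking such a drug would not count as a departure from them, so nothing in them would prompt a site to stop the drug or flag the subject.

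**Working it through.** The protocol has no figure to reproduce here. The check is an item-by-item comparison of the entry restrictions with the on-study lists, all in v7.0.

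**Item counts**
- Exclusion 10: 12 serotonergic bullets + MAOIs (in the lead-in) + 4 others = 17 items.
- Section 9.4.6 list: 13 serotonergic (MAOIs now a bullet) + 4 others = 17 items.
- Synopsis list: 13 + 4 = 17 items.

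**Side by side**

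| Entry restriction | Section 9.4.6 | Synopsis list |
|---|---|---|
| Exclusion 9: weight-loss products | Barred | Barred |
| Exclusion 10: 17 items | 17 of 17 matched | 17 of 17 matched |
| Exclusion 11: valvulopathy class | Absent | Absent |
| Exclusion 11: four named drugs | 0 of 4 | 0 of 4 |

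The match for exclusion 10 is by bullet. Topiramate is named in exclusion 10 and not in the on-study lists, but its class, antiseizure medications, remains.

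**Could another entry cover them?** Both lists are introduced as specific items, so the serotonergic heading does not extend them to unlisted agents. The nearest entry, antipsychotics and other dopamine antagonists, names neither the valvulopathy class nor any of the four drugs.

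**Does another section bar them on treatment?** None was found in Sections 9.3.3, 9.4, 9.5.1.5 or 9.5.5, or in Table 2 and its footnotes. Inclusion and exclusion criteria are checked again at Visit 2, but exclusion 11 as worded looks only at the period before Screening, so a drug started between Screening and Visit 2 falls outside it.

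**How long could use overlap?** Dosing lasts at most 52 weeks, so a drug started at Week s overlaps study drug for at most 52 − s weeks. For example, a start at Week 20 gives at most 52 − 20 = 32 weeks, of which 28 − 20 = 8 precede the Week 28 echocardiogram.

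**The case against.** The strongest reply is that exclusion 11 and Section 9.4.6 do not contradict each other. Both can be followed as written, and silence in a prohibited list leaves a drug to the investigator's judgment; it does not approve it. That stands, and the point is one of design. The protocol did not, however, rely on judgment for the drugs in exclusions 9 and 10.

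There are also real safeguards. Section 9.4.6 says "Any medication (including OTC medications) or therapy administered to the subject during the study (starting at the date of informed consent) will be recorded". Under Section 9.5.7 the investigator asks at each visit about care from other physicians and, with the subject's consent, tells the other physician about the trial, which may reach the prescriber. Section 9.5.1.5.1 has causality assessment consider factors other than study drug. Section 9.3.3 lets the investigator withdraw a subject for safety. These narrow the gap; each records, informs or responds, and none prohibits.

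Three stronger readings are tempting and are not supported:
- **A year of co-use.** The full 52 weeks would require a drug started after Screening and already in use at the first dose. Anyone who used one in the 6 months before Screening is excluded, and a later start shortens the overlap.
- **A lone slip in an otherwise complete carry-forward.** Exclusions 17 (recreational drugs) and 25 (investigational products) also concern drug use and are absent from the Section 9.4.6 list. The documents do not show that exclusion 11 was simply overlooked.
- **A biased valvulopathy comparison.** The protocol gives no rate of use, no risk given use and no reason for use to differ by arm. Safety is summarised without hypothesis testing.

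Finally, the version is uncertain. The file is part 2 of 3 and opens with the end of another copy placed before v7.0, so a later version may already differ. The itemised list in Section 9.4.6 has the same gap in v6.0 and v5.0, but that says nothing about a later text.

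**Conclusion.** The gap is real in v7.0: these drugs are barred before Screening and not barred during treatment, so a subject could take one with study drug without breaching the protocol. It is small. Use is probably rare, which is a judgment because the protocol gives no rate, and no expected number of cases can be derived. No bias and no changed trial conclusion are claimed. The case for acting is subject safety and clearer attribution of any new valve lesion. It is an optional improvement, held with medium confidence because the current version may not be among the parts shown.

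**What to change.** First check the current protocol version. If the omission remains, add one item to the prohibited lists in Section 9.4.6 and the synopsis, repeating exclusion 11's class description and its four examples (pergolide, ergotamine, methysergide, cabergoline) as an open list.

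Apply the ban while the subject is taking study drug. It should not run to the last echocardiogram regardless of treatment status: subjects who stop study drug early are followed to study completion, and that wording would restrict their care after study drug had ended. If one of these drugs becomes medically necessary, stop study drug, continue follow-up and keep the subject in the analysis. This fits the Full Analysis Set, which includes all randomised subjects whatever their adherence. A ban that starts with study drug also reaches anyone who began such a drug between Screening and randomisation.

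The cost is one bullet in each of two lists, with no new visit, test or change in sample size. The downside is that a subject may occasionally lose a treatment option or have to stop study drug.

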9.3.2 Exclusion Criteria

Subjects who meet any of the following criteria will be excluded from this study:

1. Clinically significant new illness within 1 month before randomization that may affect the subject's ability to fulfill the study requirements or significantly confound the assessments
2. Subjects who cannot swallow investigational products
3. Any of the following findings on screening echocardiography:
 - Aortic regurgitation mild or greater

- Mitral regurgitation moderate or greater
 - Mitral or aortic valve stenosis greater than mild (ie, aortic stenosis [AS]: jet >3.0 m/s, mean gradient >25 mm Hg, and aortic valve area [AVA] <1.5 cm²; MS: mean gradient >5 mm Hg and mitral valve area [MVA] <1.5 cm²)
 - Systolic pulmonary artery pressure (SPAP) >40 mm Hg (and/or tricuspid regurgitation (TR) jet velocity >2.9 m/s)
 - In cases where an actual SPAP value is not measurable due to lack of adequate TR jet, the pulmonary flow acceleration time measured at the right ventricular outflow tract (RVOTAT), will be used to assess eligibility. Patients with a RVOTAT ≤100 msec will be excluded, suggesting an elevated mean SPAP; eligibility for the those patients with RVOTAT between 100 and 120 msec will be determined based on combined assessment of the TR jet, septal motion and right ventricular size.
 - Left ventricular ejection fraction <45%
 - Intracardiac mass, tumor or thrombus
 - Evidence of congenital heart disease
 - Clinically significant pericardial effusion (eg, moderate or larger or with hemodynamic compromise)
4. Significant renal or hepatic disease as evidenced by a serum creatinine greater than 1.5×upper limit of normal (ULN), serum transaminases greater than 3×ULN, or total bilirubin greater than 1.5×ULN in absence of Gilbert’s syndrome
 5. Any history of anorexia or bulimia within 2 years before Screening, Attention Deficit Hyperactivity Disorder, any Diagnostic and Statistical Manual of Mental Disorders, 5th Edition depressive disorder, bipolar disorder, or schizophrenia
 6. Any suicidal ideation with intent with or without a plan, at the time of or within 6 months of Screening, as indicated by answering “Yes” to questions 4 or 5 on the Suicidal Ideation section of the C-SSRS.
 7. Any suicidal behavior in the past based on the C-SSRS (revised per Amendment 01)

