 19. Known to have active viral hepatitis (B or C) (revised per Amendment 01)
 20. Malignancy within 5 years before Screening
 21. Unable to attend scheduled visits (eg, lack of transportation) or lack of a caregiver or guardian to supervise study participation
 22. Special needs subjects who are unable to comprehend study-related instructions (eg, mild to profound mental retardation [IQ <70], moderate to severe cognitive developmental delay, pervasive development disorders, autism)

23. Ongoing epilepsy or other seizure disorder, or use of medications for a seizure disorder within 6 months of screening or any time between screening and randomization
24. Subjects with a BP in the 95th percentile or greater for age, sex, and height on 2 separate readings recorded on 2 separate days. Those subjects who had uncontrolled hypertension at Screening can be rescreened more than 1 month after initiation or adjustment of antihypertensive therapy 1 time.
25. Currently enrolled in another clinical study or has used any investigational drug or device within 30 days before providing informed consent
26. Planned bariatric surgery during the study
27. Not suitable to participate in the study in the opinion of the investigator, including consideration of any existing physical, medical, or mental condition that prevents compliance with the protocol
28. Female subjects who are breastfeeding or pregnant at Screening or Baseline (as documented by a positive β -human chorionic gonadotropin test). A separate Baseline assessment is required if a negative screening pregnancy test was obtained more than 72 hours before the first dose of study drug.
29. Female subjects of childbearing potential who:
 - a. Had unprotected sexual intercourse within 30 days before study entry and who do not agree to use a highly effective method of contraception (eg, total abstinence, an intrauterine device, a double-barrier method [such as condom plus diaphragm with spermicide], a contraceptive implant, an oral contraceptive, or have a vasectomized partner with confirmed azoospermia) throughout the entire study period and for 28 days after study drug discontinuation
 - b. Are currently abstinent, and do not agree to use a double-barrier method (as described above) or refrain from sexual activity during the study period and for 28 days after study drug discontinuation

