 - c. Are using hormonal contraceptives but are not on a stable dose of the same hormonal contraceptive product for at least 4 weeks before dosing and who do not agree to use the same contraceptive during the study and for 28 days after study drug discontinuation

(NOTE: All female subjects will be considered to be of childbearing potential unless they have been sterilized surgically [ie, bilateral tubal ligation, total hysterectomy, or bilateral oophorectomy, all with surgery at least 1 month before dosing]).

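### Read literally, exclusion 29 lets a sexually active female whose recent intercourse was protected refuse all contraception and still be eligible

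*Protocol*

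**What the plan says.** The lead-in to Protocol section 9.3.2 makes each criterion sufficient on its own: "Subjects who meet any of the following criteria will be excluded from this study". No. 29 then lists three kinds of female of childbearing potential:

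- 29a: those who "Had unprotected sexual intercourse within 30 days before study entry and who do not agree to use a highly effective method of contraception". The list of acceptable methods includes total abstinence, an intrauterine device, double barrier, implant, oral contraceptive and a vasectomised partner.
- 29b: those who "Are currently abstinent, and do not agree to use a double-barrier method" or to refrain from sexual activity.
- 29c: those who "Are using hormonal contraceptives but are not on a stable dose of the same hormonal contraceptive product for at least 4 weeks before dosing". To this the item joins a further condition about refusing to continue the product, worded "and who do not agree to use the same contraceptive during the study".

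The commitment in each item covers the study and 28 days after study drug. A closing note makes the population nearly universal: "All female subjects will be considered to be of childbearing potential unless they have been sterilized surgically".

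The Synopsis repeats No. 29 with the same structure, for example "Are using hormonal contraceptives, but are not on a stable dose of the same hormonal contraceptive product" followed by the same joined condition. The wording is also the same in v6.0 (No. 29), v5.0 (No. 27) and the v4.0 Synopsis (No. 27).

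**The concern.** The note, the 28-day tail and the rule in section 9.5.4.2 that a pregnant subject must be withdrawn all suggest that every non-sterilised female was meant to commit to contraception or abstinence. The text does not say that. Refusal excludes only in company with another fact, and the three accompanying facts do not cover all females. The rule therefore binds the abstinent girl, who is at least current risk, and misses some who are sexually active.

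Nothing else shown supplies the requirement. Section 9.3.1 has no contraception criterion. Exclusion 27 is investigator discretion, applied site by site at about 30 sites. Exclusion 28 requires a recent negative pregnancy test ("A separate Baseline assessment is required if a negative screening pregnancy test was obtained more than 72 hours before the first dose"), and Table 2 repeats the test, but testing finds a pregnancy after conception. The subjects are 12 to 17 years old and may take study drug for up to 52 weeks.

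**Working it through.** The plan gives no figure to reproduce. The check is logical.

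**Inputs.** The lead-in to section 9.3.2 and items 29a to 29c, with *and* read as joining two conditions that must both hold:

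- 29a = unprotected intercourse within 30 days AND no agreement to a listed method
- 29b = abstinent AND no agreement to double barrier or refraining
- 29c = hormonal user AND not stable for 4 weeks AND no agreement to keep the product
- Excluded = 29a OR 29b OR 29c

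**Case tested.** A non-sterilised female who refuses every commitment, so each agreement is false. Abstinence and recent unprotected intercourse are taken as mutually exclusive, and no intercourse in the last 30 days is counted as abstinent.

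| Last 30 days | No hormones | Hormonal, under 4 weeks stable | Hormonal, 4 weeks or more stable |
|---|---|---|---|
| Abstinent | excluded (29b) | excluded (29b, 29c) | excluded (29b) |
| Protected intercourse only | **eligible** | excluded (29c) | **eligible** |
| Unprotected intercourse | excluded (29a) | excluded (29a, 29c) | excluded (29a) |

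Of 9 logical states, 7 are excluded and 2 are eligible. These are states, not subjects.

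The stable hormonal user in the middle row is the girl who will stop her product and replace it with nothing. An oral contraceptive and an implant are themselves on the 29a list, so intercourse while using them naturally counts as protected. A stable user who changes to another listed method still has contraception and is not part of the problem.

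**After the fix.** If 29a becomes *no agreement to a listed method* with no precondition, it is true in all 9 cells and every refuser is excluded, with 29c unchanged.

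**How long a pregnancy could go untested.** Table 2 schedules urine tests after Screening at Weeks 0, 1, 5, 8, 12, 20, 28, 36, 44, 52 and 56. The gaps are 1, 4, 3, 4, 8, 8, 8, 8, 8 and 4 weeks. The longest is 8 weeks and occurs five times in a row between Weeks 12 and 52. With the ±7-day visit window at both ends it can reach 8 + 2 × 1 = 10 weeks.

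**The case against.** The strongest reply is grammatical. The stem of No. 29 already ends in *who*; 29a and 29c repeat that pronoun after *and*, while 29b does not. The repeated pronoun can be attached to the stem, opening a second class: 29a would then exclude girls with recent unprotected intercourse and, separately, girls who do not agree to contraception. Every refuser is caught on that reading. It would also bar a girl with recent unprotected intercourse who does agree, which a sponsor could defend because one test soon after intercourse may miss an early pregnancy. This stands as a possible reading. The conjunctive reading is the more natural one, and two readings that give opposite eligibility for the same girl are themselves a reason to reword.

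Other limits also stand. *Unprotected* is not defined, so the non-hormonal gap shrinks if a site counts condom-only intercourse as unprotected; the stable-user gap closes if a site counts intercourse on hormones without a barrier that way. Exclusion 27, the test within 72 hours before first dose, the repeated tests and withdrawal on pregnancy all limit the consequence, though none is a contraception rule. The file shown is one part of three and opens with the closing sections of another copy placed ahead of v7.0, so a later version with its own No. 29 may exist.

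A reader might also infer that 29c needs *or* in place of *and*, because a girl newly on a hormonal product who agrees to continue is not excluded and the 4-week lead-in never acts alone. The documents do not support making that part of this point. She has made the commitment. Enforcing the lead-in would bar a girl three weeks into an oral contraceptive who will keep taking it, while a girl using nothing who promises to start one at dosing would satisfy the new 29a.

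**Conclusion.** The point holds as a wording fault in exclusion 29. On the literal reading, the written rule gives the wrong eligibility result for two kinds of sexually active female; on the alternative reading it is ambiguous. It deserves correction because it concerns the safety of minors and the correction is cheap.

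Its size in subjects cannot be stated. The protocol gives no figure, and the number is probably small, since both groups are girls currently using protection who would have to refuse every listed method. It would be wrong to infer that many subjects are exposed, that efficacy inference suffers (power and alpha are unaffected), or that the final protocol certainly contains the fault.

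The conclusion assumes that *and* in 29a and 29c is conjunctive, that protected intercourse includes intercourse on a listed hormonal method, and that no contraception rule stands in text not shown.

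**What to change.** In section 9.3.2 and in the Synopsis:

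1. Make 29a a stand-alone exclusion for every non-sterilised female: she does not agree to use one of the listed highly effective methods, continued total abstinence included, for the whole study and for 28 days after stopping study drug. Drop the 30-day unprotected-intercourse clause as a precondition. A girl who agrees and tests negative under No. 28 then stays eligible. If the sponsor wants recent unprotected intercourse to bar entry by itself, it should say so in a separate item.
2. Align 29b so that an abstinent subject may commit to continued abstinence or to any method in the 29a list. Left as it is, 29b would exclude an abstinent girl who commits to an intrauterine device, implant or oral contraceptive, although she satisfies the new 29a.
3. Leave the *and* in 29c alone for this purpose. Whether to enforce the 4-week hormonal lead-in on subjects who agree to continue is a separate choice.

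The cost is a wording change in two places through the amendment process in section 11.1, and the few candidates who refuse all contraception become ineligible.
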